## L.2.2 Major Adverse Events (MAEs)

Respiratory complications	
Atelectasis	
Collapse of part or (much less commonly) all of a lung caused by a blockage of the air passages (bronchus or bronchioles) or by pressure on the outside of the lung.
 
Clinical evidence of atelectasis is determined by physical, radiographic, and laboratory findings requiring treatment with antibiotics, inhalation therapy, intubation, or suctioning.

Pneumonia	
Inflammation of the lung, usually caused by an infection.
 
Clinical evidence of pneumonia is determined by physical, radiographic, and laboratory findings requiring treatment with antibiotics, inhalation therapy, intubation, or suctioning.

Pulmonary embolism	Sudden onset of pleuritic chest pain, cough, hemoptysis, hypoxia, tachycardia and a positive ventilation/perfusion (V/Q) scan.
Pulmonary edema	Abnormal accumulation of fluid in the lungs.
Respiratory failure	The need for ventilatory support for >72 hours associated with an inability to wean from the respirator for any reason.
Renal complications	
Renal failure	Sudden reversible failure of renal function caused by shock, interruption of blood flow to the kidneys, direct damage to the kidney's and/or sudden obstruction of urine flow.
Renal insufficiency	Slowly progressive failure of renal function resulting from some disease (e.g., diabetes, cancer, hypertension, glomerulonephritis) that causes gradual destruction of the kidneys or if creatinine levels are available, an increase of >25% above the pre-procedure creatinine level.
Cardiac complications	
Myocardial Infarction (MI)	
 
Non-Q-wave MI is defined as elevated CK > 2X the upper lab normal with the presence of elevated CK-MB (any amount above the institutions upper limit of normal) in the absence of new pathological Q waves.
 
Q wave myocardial infarction is defined as development of new, pathological Q waves in 2 or more contiguous leads (as assessed by the ECG core laboratory) with post-procedure CK elevation >2x ULN and CKMB levels elevated above normal.
 

Unstable angina	Chest pain unrelieved by anti-anginal medications in a subject with known coronary artery disease without significant elevations in cardiac enzymes.

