New arrhythmia	The development of new atrial arrhythmia, new ventricular arrhythmia, exacerbation of a prior arrhythmia, a significant increase in severity of a current arrhythmia or any episode of cardiac arrest.
Congestive Heart Failure (CHF)	Failure of the heart to pump blood with normal efficiency. Development of an acute episode of or exacerbation of existing low cardiac output or fluid overload accompanied by peripheral and/or pulmonary edema.

Central and peripheral neurological complications	
Cerebrovascular accident (CVA) / Stroke	Defined as sudden onset of vertigo, numbness, aphasia, or dysarthria due to vascular lesions of the brain such as hemorrhage, embolism, thrombosis, or rupturing aneurysm, that persisted >24 hours.
Cerebrovascular Embolic event	The obstruction of a blood vessel from the brain by a blood clot or foreign substance (e.g. air, fat, bacteria).
Paraplegia	Complete loss of motor function in the lower extremities and lower portions of the trunk. A thoracic or lumbar injury can affect leg, bowel and bladder control and sexual function.
Paraparesis	Mild loss of bilateral lower extremity motor function; bilateral lower extremity weakness.
Gastrointestinal complications	
Bowel ischemia	A decrease in blood supply to either the large or small intestine that is associated with pain, bleeding, abdominal distension, diarrhea or x-ray or angiographic evidence of reduced organ flow.
Major Bleeding complications	
Bleeding, procedural	A blood loss greater than 750 cc occurring before the subject leaves the OR.
Bleeding, post-procedural	Post-procedural bleeding greater than 750cc occurring after the subject leaves the OR.
Coagulopathy	The development of an abnormal bleeding disorder (e.g., Disseminated Intravascular Coagulopathy or Thrombocytopenia with platelet counts of < 80,000) documented by appropriate laboratory studies requiring therapy with medication or transfusion.
Vascular complications	
Aortic rupture	The tearing apart of the aortic tissue. Signs of aortic rupture include hemothorax, unrelenting chest or back pain, or hypotension refractory to medical management for a period exceeding two (2) days.
Aneurysm rupture	See definition of Thoracic Aortic Aneurysm rupture in section L.2.1

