7.7. Treatment Characteristics

The following acute procedural observations and clinical utility measures will be analyzed using descriptive statistics:

- Mean duration (min) of procedure
- Proportion of subjects who underwent general anesthesia
- Proportion of subjects who underwent percutaneous access
- Proportion of subjects requiring blood transfusions

- Mean number of units of blood transfused, if required
- Mean volume (cc) of estimated blood loss
- Mean length of time (hours) in intensive care unit
- Mean length of time (days) of hospital stay (from the index procedure to hospital discharge)

Study device disposition will be summarized by type and size. Number of study devices used on each subject will be analyzed descriptively.

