k = No. of Subjects Who Had No MDE	No. of subjects who have been in study for at least 1 day and without an MDE.	No. of subjects who have been in study for at least 91 days and without an MDE.	No. of subjects who have been in study for at least 305 days and without an MDE.

If a subject is early terminated from the study, the last day that the subject has been seen will be the duration in study, which can be the day of last follow-up, last imaging taken, an AE reported, or withdrawal from the study. If a subject is still in the study, the duration in study will be the time from index procedure to the cut off day that the database is locked or data snapshot is taken.

Subgroup analyses by-sex, by-race (based on subjects enrolled in the US only, since collection of race and ethnicity data may not be allowed outside the US as per local law and regulation), FreeFlo versus Closed Web configuration as proximal component, percutaneous access versus non-percutaneous, and by-region/study site will be performed on the primary study endpoint using descriptive statistics and reviewed for

clinical significant difference.

Secondary Endpoints

30-day Secondary Endpoint

The following secondary endpoints will be evaluated within 30 days post treatment:

- Peri-operative mortality
- All adverse events (AE) within 30 days including:
 - Major Adverse Event(s) (MAE)
 - Serious Adverse Event(s) (SAE)
- Secondary procedures
- Loss of stent graft patency at 30 day visit based on imaging findings
- Endoleaks at 30 day visit based on imaging findings

Detailed definitions of MAEs are defined in the Clinical Investigational Plan Appendix L.2.2. MAEs will be identified using codes in the Medical Dictionary for Regulatory Activities (MedDRA) provided by the Medtronic Clinical Safety group.

6-month Secondary Endpoints:

The following secondary endpoints will be evaluated:

- All-cause mortality within 183 days
- Aneurysm-Related Mortality within 183 days
- MDEs within 183 days
- All AEs within 183 days including:
 - MAEs
 - SAEs
- Secondary procedures within 183 days
- Loss of stent graft patency within 6 months based on imaging findings
- Endoleaks at 6 months based on imaging findings

- Stent graft migration at 6 months as compared to 1-month imaging
- Aneurysm expansion > 5mm at 6 months based on imaging findings relative to the 1-month visit

12-month Secondary Endpoints

The following secondary endpoints will be evaluated:

- All-cause mortality within 365 days

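### SAP 7.9 identifies MAEs by MedDRA code and states no step that applies the Appendix L.2.2 criteria, so the MAE rates can be misclassified for the threshold-based components

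*SAP*

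**What the plan says.** SAP 7.9 lists MAEs among the secondary endpoints at 30 days, 6 months and 12 months. It deals with their definition and identification in two consecutive sentences. The first points to the protocol: "Detailed definitions of MAEs are defined in the Clinical Investigational Plan Appendix L.2.2". The second gives the rule to follow: "MAEs will be identified using codes in the Medical Dictionary for Regulatory Activities (MedDRA) provided by the Medtronic Clinical Safety group". SAP 3 describes the SAP as a guide for the study biostatistician and the programmers.

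Several definitions in Protocol L.2.2 rest on a measured amount or duration. Procedural bleeding is "A blood loss greater than 750 cc occurring before the subject leaves the OR", and the same volume applies after the subject leaves the operating room. Respiratory failure is "The need for ventilatory support for >72 hours associated with an inability to wean from the respirator for any reason". Stroke requires symptoms "that persisted >24 hours". Renal insufficiency may be established by "an increase of >25% above the pre-procedure creatinine level".

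Procedural blood loss is collected, but SAP 7.7 uses it only as a summary: "Mean volume (cc) of estimated blood loss".

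**The concern.** A MedDRA code classifies the term that the site reported. It does not record how much blood was lost, how long ventilation lasted or how far CK rose. A 300 cc bleed and a 900 cc bleed can carry the same code. If the list includes that code, both count as MAEs. If it leaves the code out, both are lost. No choice of list reproduces the 750 cc line.

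At stake is the meaning of a secondary safety endpoint in data meant to support PMA approval. For these components the rate would depend partly on how sites word their events. SAP 7.3 assumes that the US and International data can be pooled, partly because event definitions are similar, but its planned poolability review covers the primary endpoint only. A difference in wording between sites could go unnoticed in the MAE rates.

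**Working it through.** The documents state no expected MAE rate and no MAE sample size or power, so there is no planned figure to reproduce. The check compares the passages.

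**1. Which terms need more than a code.** Protocol L.2.2 defines 27 terms: 5 respiratory, 2 renal, 4 cardiac, 4 neurological, 1 gastrointestinal, 3 bleeding or coagulation and 8 vascular (5 + 2 + 4 + 4 + 1 + 3 + 8 = 27). Seven carry a numeric cut-off.

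| Term | Criterion in L.2.2 | Status of the cut-off |
|---|---|---|
| Procedural bleeding | above 750 cc | required |
| Post-procedural bleeding | above 750 cc | required |
| Respiratory failure | ventilation beyond 72 h | required |
| Stroke | lasting more than 24 h | required |
| Myocardial infarction | CK above twice the upper limit, with raised CK-MB | required |
| Renal insufficiency | creatinine up by more than 25% | one of two routes, if levels are available |
| Coagulopathy | platelets below 80,000 | given as an example; therapy also required |

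The other 20 terms (27 − 7) have no numeric cut-off of this kind, apart from a two-day duration within the signs listed for aortic rupture. Most are diagnoses that a code can capture, such as paraplegia, pulmonary edema and arteriovenous fistula. Atelectasis and pneumonia also require treatment.

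**2. Whether sub-threshold events reach the database.** They do. Protocol F.6.2 requires every adverse event to be reported except those in Table F-3. That table does not exempt bleeding other than mild to moderate bruising, nor respiratory failure, nor creatinine rises.

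**3. Whether another step applies the criteria.** None is stated.
- Protocol F.6.6 names MDEs, deaths and DTAA ruptures as the events the CEC adjudicates. MAEs in general are not named.
- Protocol F.6.4 has the sponsor review all adverse events, but the only content it names is whether an event is reportable to regulators.
- SAP 7.9 states that MDEs are adjudicated by the CEC and says nothing equivalent for MAEs.

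**4. How an error would enter the rate.** SAP 7.9 calculates non-image event rates as in Table 5, m/(m + k), where m counts subjects with at least one event. A misclassified event therefore changes the rate only if that subject has no other qualifying MAE. With 100 evaluable subjects, one such subject moves the rate by 1/100 = 1 point.

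**5. Illustration on assumed inputs.** None of these values comes from the documents. Let T be the true proportion of subjects with an MAE, S the share of them that the codes flag, and F the share of MAE-free subjects flagged for a sub-threshold event. The reported rate is T × S + (1 − T) × F. For example, T = 20%, S = 1 and F = 5% gives 0.20 × 1 + 0.80 × 0.05 = 24%.

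| T | S = 0.9, F = 0 | S = 1, F = 5% | S = 1, F = 10% | S = 0.9, F = 5% | S = 0.9, F = 10% |
|---|---|---|---|---|---|
| 20% | 18% | 24% | 28% | 22% | 26% |
| 30% | 27% | 33.5% | 37% | 30.5% | 34% |
| 40% | 36% | 43% | 46% | 39% | 42% |

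The difference from T runs from −4 points (36% − 40%) to +8 points (28% − 20%). The table shows only that the sign is not fixed.

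**The case against.** The strongest reply is that the SAP keeps L.2.2 as the definition, in the sentence directly before the coding rule. The codes come from the sponsor's safety group, which could check each event against L.2.2 before an MAE is flagged. The code list, the adverse event eCRF, the CEC charter and the US protocol are not supplied, and the charter may name further events for adjudication. Protocol F.6.1 also speaks of reporting events that meet the study definitions. All of this is fair, and it limits the point to an unstated step. It does not remove the point, because the SAP is the programmers' guide and the only rule it gives them is the code.

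A reader might go further and infer that the MAE endpoint as a whole will not be measured, or that every coded bleed counts whatever its size. The documents do not support that. Twenty of the 27 terms have no such cut-off. Access-site hematoma and retroperitoneal bleed count at any size, so many smaller bleeds are true MAEs. The contents of the code list are also unknown.

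A reader might also put a definite overstatement on the rate. For instance, if 20 of 100 subjects had coded threshold-type events and 20–40% of those fell short of L.2.2, the excess would be 4–8 points (20 × 0.2 = 4; 20 × 0.4 = 8). Those inputs have no source. The result is also an upper bound, because some of those subjects may have another qualifying MAE.

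Finally, a blood loss above 750 cc that appears only on the procedure form would be a site reporting failure under F.6.2, not a result of the SAP rule itself. That is correct. The volume is nevertheless collected, and the plan does not use it to catch such a case.

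**Conclusion.** The point holds in limited form. For the seven threshold-based terms, the stated identification rule and the stated definition differ, and no stated step reconciles them. The cut-off is only part of the definition for two of these, renal insufficiency and coagulopathy. The MAE rates at 30 days, 6 months and 12 months can be misclassified in either direction on these components.

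The documents give no size for the error, and none should be quoted as a finding. SAP 7.9 plans no inference on secondary endpoints. The primary endpoint is built on access and deployment failures and CEC-adjudicated MDEs, so its type I error and power are untouched.

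The conclusion rests on one assumption. The SAP serves the US protocol, which is not supplied, so the thresholds here are those of the International protocol's L.2.2. SAP 7.3 says the event definitions in the two protocols are similar. The matter should be settled before the analysis but does not threaten the trial's main conclusion.

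**What to change.** Amend SAP 7.9 as follows.
- Use the MedDRA list as a first search for candidate MAEs.
- Derive procedural major bleeding directly from the recorded estimated blood loss, at more than 750 cc.
- For the other threshold-based terms, have the sponsor's safety group flag whether each coded event meets L.2.2, using data already on the adverse event eCRF.
- Keep an event as an MAE when the needed measurement is missing. Protocol Table F-2 schedules no laboratory tests, so a rule that counted only confirmed events would drop real safety events for lack of a value.
- Report the code-only rate as a sensitivity analysis, so that the effect of the check can be seen.

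The cost is one derived variable, one flag per coded threshold-type event, and a small amount of event-level checking in about 100 subjects. The eCRF is not supplied, so what it holds for each term should be confirmed first. Where it lacks the value, the missing-measurement rule applies.

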Subjects will be followed until the last subject enrolled has completed the 1 year follow-up visit or until PMA approval is obtained in the US (whatever is later), however, Medtronic will work with FDA to determine if longer term follow after PMA approval is required. A post-approval analysis of 1-year Major Device Event (MDE) rate is planned.

6. Determination of Sample Size

One hundred (100) enrolled subjects will ensure 87 evaluable subjects at 30 days. The primary endpoint analysis will be completed upon 87 evaluable subjects reaching the 30 day endpoint. Based on Valor II study results, Valiant Evo is expected to perform similarly and have 6% of MDE combined with access and/or deployment failures at 30 days. The sample size of 87 evaluable subjects will provide 85% statistical power for the study hypothesis. The type I error is controlled at the one-sided 0.025 level.

Table 1: Power Analysis

True rate of MDEs combined with access and/or deployment failures at 30 day with Valiant Evo	6%
Performance Goal	16%
Significance level	0.025
Statistical test	One-sided binomial test
Evaluable sample size	n=87
Enrollment	Minimum of 100 subjects enrolled to ensure 87 evaluable subjects
Statistical power from the 87 evaluable subjects	85%

One hundred (100) enrolled subjects will also ensure 63 evaluable subjects at 1-year on MDE rate for the post-approval analysis. The VALOR II study with the Valiant stent graft system enrolled 160 patients with DTAA and was assessed through 12 months for purposes of PMA (P100040) approval. Through 1-year post-

treatment, the rate of MDEs combined with access and/or deployment failures was 7.1% (11/153) (Medtronic internal data using the Valiant Evo proposed definition). Therefore, for the purpose of post approval analysis, the rate of MDEs combined with access and deployment failures at 1-year with Valiant Evo is estimated to be 7.1% (refer to Table 22 below for power analysis assumptions).

Table 2: Power Analysis for Post-approval Analysis of 1-year Endpoint

Estimated rate of MDEs combined with access and/or deployment failures at 1 year with Valiant Evo	7.1%
Performance Goal (PG) at 1-year	20%
Significance level	0.05
Statistical test	One-sided binomial test
Evaluable sample size	N = 63 at 1 year
Enrollment	IDE cohort will enroll a minimum of 100 subjects and is expected to have a minimum of 63 evaluable subjects at 1-year follow up.

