7.9. Evaluation of Objectives

Primary Endpoint

The primary objective will be assessed by the composite safety and effectiveness endpoint that is based on the proportion of subjects who experienced:

- (a) Access and/or deployment failures; and/or
- (b) Major device effects (MDE) within 30 days post index procedure

MDEs include the occurrence of any of the following:

- Device-related secondary procedures
- Device-related mortality
- Conversion to open surgery
- Thoracic aortic aneurysm rupture

Detailed definitions of MDEs are defined in Clinical Investigational Plan Appendix L.5.

The primary study endpoint will be tested against a performance goal of 16% at 30 days:

$$H_0: p \geq 16\% \text{ vs. } H_a: p < 16\%,$$

where p denotes the true event rate of primary study endpoint in the target population. If the null hypothesis

(H₀) is rejected at the one-sided 0.025 statistical significance level, it is considered that the performance goal for the primary endpoint has been reached.

The analysis set of all enrolled subjects will be used for the analysis. The primary study endpoint is a dichotomous study outcome; hence, an exact method based on the binomial distribution will be used for the hypothesis testing.

Primary Endpoint Calculation:

A subject will be a failure on the primary endpoint if the subject either failed on access/deployment or had an MDE within 30 days. A subject will be a success on the primary endpoint if the subject is confirmed for access and deployment success as well as free from MDE. The failure rate of the primary endpoint is the percent of failures in all the evaluable subjects for the endpoint, i.e., in total number of failures and successes. Note that a subject who had an MDE within 30 days is one of the subjects in m as defined below. A subject who is free from MDE is one of the subjects in k as defined below.

MDE Rate Calculation:

All MDEs will be adjudicated by the Clinical Event Committee (CEC) per study protocol. MDE rate will be calculated as follows (Table 5):

Table 5: MDE Rate Calculation:

MDE rate = $m/(m + k)$	Within 30 Days	Within 183 Days	Within 365 Days
m = No. of Subjects Who Had MDE(s)	No. of subjects who had at least one MDE with onset day from Day 0 to Day 30, inclusive.	No. of subjects who had at least one MDE with onset day from Day 0 to Day 183, inclusive.	No. of subjects who had at least one MDE with onset day from Day 0 to Day 365, inclusive.

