- Aneurysm-Related Mortality within 365 days
- MDEs within 365 days
- All AEs within 365 days including:
 - MAEs
 - SAEs
- Secondary procedures within 365 days
- Loss of stent graft patency within 12 months based on imaging findings
- Endoleaks at 12 months based on imaging findings
- Stent graft migration at 12 months as compared to 1-month imaging
- Aneurysm expansion > 5mm at 12 months based on imaging findings relative to the 1-month visit

Secondary endpoints are to be assessed beyond 12 months. The following secondary endpoints are to be evaluated at 24, 36, 48, and 60 months:

- All-cause mortality
- Aneurysm-Related Mortality
- MDEs
- All AEs and SAEs
- Secondary procedures
- Loss of stent graft patency based on site reported imaging findings
- Endoleaks based on site reported imaging findings

- Stent graft migration as compared to 1-month imaging
- Aneurysm expansion > 5mm based on site reported imaging findings relative to the 1-month visit

Health-related quality of life outcomes are to be assessed at all scheduled follow-up visits using the EQ-5D questionnaire.

Stent graft migration will be determined by the core lab or site imaging case report from (CRF). Core lab assessment and site reported result will be analyzed separately. Aneurysm expansion will be calculated. When 1-month image is not available, the latest image taken prior to 1-month will be used for calculation.

Descriptive statistical analyses will be performed on secondary endpoints. No inferential statistical analysis is planned for secondary endpoints.

Non-image endpoints event rates such as mortality, secondary procedures, MAEs, SAEs, conversion to open surgery, and thoracic aortic aneurysm ruptures through 1 year will be calculated in the same way as the MDE rate, specified in Table 5. The event rates beyond 1 year through 5 years will be analyzed using Kaplan Meier method.

Imaging based Event Rate Calculation:

Unless otherwise specified, imaging assessment will be performed by site as well as the core lab. Assessments from the core lab will be the primary result for the PMA and PMA-s submissions and analyzed separately from those by site. Imaging based event rate will be calculated using statistical analysis windows as follows (Table 6):

Table 6: Imaging based Event Rate Calculation:

Event rate = m/n	At 1 Month	At 6 Months	At 12 Months

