m = No. of Subjects Who Had Event(s)	No. of subjects who had an event with scan day within the 1-month window.	No. of subjects who had an event with scan day within the 6-month window.	No. of subjects who had an event with scan day within the 12-month window.
n = No. of Subjects Who Had Readable Images	No. of subjects who had a readable image within the 1-month window.	No. of subjects who had a readable image within the 6-month window.	No. of subjects who had a readable image within the 12-month window.
Event rate = m/n	Through 1 Month	Through 6 Months	Through 12 Months
m = No. of Subjects Who Had Event(s)	No. of subjects who had an event with scan day within the 1-month window.	No. of subjects who had an event with scan day within 1- or 6-month windows.	No. of subjects who had an event with scan day within 1-, 6- or 12-month windows.
n = No. of Subjects Who Had Readable Images	No. of subjects who had a readable image within the 1-month window.	No. of subjects who had an event (counted in m) or had a readable image within the 6-month window.	No. of subjects who had an event (counted in m) or had a readable image within the 12-month window.

The imaging based event rates by visit at 24, 36, 48 and 60 months will be calculated in a similar way as above; i.e., m = number of subjects who had an event with scan day within the statistical analysis window of the specific time point; n = number of subjects who had a readable image within the 12-month window.

The cumulative event rate through 24, 36, 48 and 60 months will be estimated using survival analysis. Kaplan-Meier estimates, along with its standard error using the Greenwood method, will be reported for non-image based events. The image-based events are interval censored data and the interval censored survival analysis method will be used to calculate the event rates.

When reporting the site reported endoleaks, both site imaging findings and the events treated during secondary procedures will be accounted for in the analysis.

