7.10. Safety Evaluation

All adverse events (AE) will be coded using the Medical Dictionary for Regulatory Activities (MedDRA) and categorized by System Organ Class (SOC) and Preferred Term (PT) for summary. Device-related AEs, procedure-related AEs, and serious AEs will be tabulated separately and by time period. The denominator in event rate calculation will be based on the number subjects available at the beginning of each time period. The relationship to device and procedure as well as seriousness will be based on site-reported data from the AE case report form (CRF).

The survival from all-cause mortality and aneurysm-related mortality over one year time or longer will be described by the Kaplan-Meier survival curve and the associated Kaplan-Meier estimate will be calculated along with its standard error using the Greenwood method.

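### SAP 7.9 and 7.10 give one-year mortality two estimators without naming the reported one, and the Table 5 rule is biased by when subjects leave

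*SAP*

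**What the plan says.** - **SAP 7.9, secondary endpoints.** Rates of mortality, secondary procedures, MAEs, SAEs, conversion and rupture "through 1 year will be calculated in the same way as the MDE rate, specified in Table 5". After that the method changes: "The event rates beyond 1 year through 5 years will be analyzed using Kaplan Meier method".
- **SAP 7.9, Table 5, 365-day column.** The rate is m/(m+k). For m the table counts "No. of subjects who had at least one MDE with onset day from Day 0 to Day 365, inclusive"; for k, "No. of subjects who have been in study for at least 305 days and without an MDE".
- **SAP 7.9, after Table 6.** "The cumulative event rate through 24, 36, 48 and 60 months will be estimated using survival analysis", with Kaplan-Meier named for the non-image events.
- **SAP 7.10.** "The survival from all-cause mortality and aneurysm-related mortality over one year time or longer will be described by the Kaplan-Meier survival curve". The associated estimate and its Greenwood standard error are to be calculated as well, so this is a number and not only a figure.
- **SAP 7.10, adverse events, serious events included.** "The denominator in event rate calculation will be based on the number subjects available at the beginning of each time period".
- **Protocol H.1** (International trial) also describes all-cause mortality over one year or longer by Kaplan-Meier.

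**The concern.** All-cause mortality within 365 days is a listed 12-month endpoint. A programmer who follows 7.9 and one who follows 7.10 produce different numbers for it whenever an event-free subject leaves before Day 305, and either could be called the planned rate.

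The Table 5 rule also treats exits unevenly. A subject who dies on Day 40 is counted. A subject who leaves alive on Day 40 vanishes from the denominator. A subject who leaves alive on Day 310 is counted as having survived the full year. The first feature inflates the rate when there are early exits, and the last deflates it.

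Secondary procedures, MAEs, conversion and rupture have only m/(m+k) at one year, so they carry the same bias and then move to Kaplan-Meier afterwards. If death ends time in study, a subject who dies before Day 305 without the non-fatal event is also removed from k. Serious adverse events meet a second denominator in 7.10.

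At stake are the clarity and accuracy of the one-year rates in a report that supports PMA approval.

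**Working it through.** **The plan's own figure.** The documents give no figure for this bias. The only stated figure that rests on the one-year evaluable set is the 92% power in SAP Section 6 (63 evaluable, 7.1% against a goal of 20%, one-sided 0.05). Exact binomial: reject at 7 or fewer events, attained level 0.0473, power 92.3%. It reproduces.

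**A hand example.** Take 100 subjects, 10 early events, then 20 event-free exits on Day 200. Here m = 10 and k = 70, so Table 5 gives 10/80 = 12.5%. Kaplan-Meier gives 10/100 = 10%, because all events precede the exits.

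**Expected size.** Assumptions: true one-year risk p, constant hazard, exit independent of risk, a fraction a leaving by Day 305 at a constant rate, and no exits after that. Neither the 10% mortality nor the loss rates stand in the documents.

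- λ = −ln(1−p)/365 and μ = −ln(1−a)/305
- m = [λ/(λ+μ)]·[1 − (1−a)(1−p)^(305/365)] + (1−a)·[(1−p)^(305/365) − (1−p)]
- k = (1−a)(1−p)

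For p = 0.10 and a = 0.20:
- λ/(λ+μ) = 0.2829 and 0.9^(305/365) = 0.9157
- m = 0.2829 × (1 − 0.8 × 0.9157) + 0.8 × (0.9157 − 0.9) = 0.0757 + 0.0126 = 0.0882
- k = 0.8 × 0.9 = 0.72
- m/(m+k) = 0.0882/0.8082 = 10.9%

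| Early loss a | m | k | m/(m+k), true 10% |
|---|---|---|---|
| 10% | 0.0942 | 0.810 | 10.4% |
| 20% | 0.0882 | 0.720 | 10.9% |
| 37% | 0.0776 | 0.567 | 12.0% |

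Simulations of 4,000 trials of 100 subjects gave 10.4% to 10.5%, 10.9% to 11.0% and 11.9% to 12.1%. Kaplan-Meier at Day 365 gave 9.9% to 10.1%.

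The 37% row comes from "One hundred (100) enrolled subjects will also ensure 63 evaluable subjects at 1-year on MDE rate", read as if all of the other 37 leave early. SAP Table 2 presents 63 as a minimum, so this row is an upper case.

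**The opposite direction.** If a further 25% of those remaining leave on Day 305 to 364, a true 10% becomes 10.2% and 10.7% at 10% and 20% early loss: still upward, but less. If late exits dominate, the sign reverses. With a true 7.1%, 5% early exits and half of the rest leaving evenly over Day 305 to 365, the rule gives about 7.0%. With no early exits and everyone leaving evenly over that interval, it gives 6.5%.

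**Competing deaths.** Take a non-fatal event with 7.1% risk in the absence of death, 10% competing deaths and 10% early exits. The true cumulative incidence is 6.7%. The Aalen-Johansen estimate averages 6.8%, Kaplan-Meier 7.1% and m/(m+k) 7.7%.

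**The case against.** - **Low consequence.** SAP 7.9 plans no inference on secondary endpoints. At 10% early loss the bias is about half a point, against a binomial standard error of √(0.10 × 0.90/100) = 3.0 points. An upward bias in adverse rates also works against the device. All of this stands and limits the severity. It does not settle which of two planned numbers is the result.
- **Complementary displays.** A crude proportion with its denominator can sit beside a Kaplan-Meier curve. That is true if one is named as the reported rate; the SAP names neither.
- **Scope.** A reader might infer that every non-image event has two estimators at one year. The documents do not support this. SAP 7.9 confines Kaplan-Meier to the period beyond one year, and 7.10 adds it only for the two mortality endpoints. For serious adverse events the second rule is a different denominator, not Kaplan-Meier.
- **Direction.** A reader might infer that Table 5 always overstates. It need not. The 12-month visit window opens on Day 305, and Protocol L.3.3.2 has International subjects who decline extension exit after that visit, so late exits are realistic.
- **Kaplan-Meier as the correct answer everywhere.** It needs independent censoring, and it overstates risk where death competes, as it does for aneurysm-related mortality and non-fatal events.
- **A falling cumulative rate.** The change of method makes a drop between 12 and 24 months possible. In the hand example, with no further events, 12.5% would become 10%. Under constant hazards it was uncommon in simulation (4% of trials or fewer), so it should not be presented as expected.
- **Protocol H.1.** The SAP names the US trial protocol as its main reference, and H.1 belongs to the International trial. The conflict therefore rests on SAP 7.9 against 7.10.

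**Conclusion.** The point holds for mortality: two sections of the SAP order two different one-year estimates, and neither is designated as the reported rate. It also holds that the Table 5 rule is biased, with a sign that depends on when subjects leave.

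Under constant hazards and independent exit, a true 10% is overstated by about 0.4 to 0.5 points at 10% early loss, 0.9 at 20% and about 2 in the 37% upper case. It is slightly understated when exits on Day 305 to 364 dominate. The other non-image events share the bias but do not have two competing one-year estimators, apart from the serious-event denominator in 7.10.

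A reader might infer that a success criterion is compromised. The text at issue covers descriptive secondary endpoints, and no test or decision rule changes. This should be corrected, but it does not threaten the trial's conclusions.

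**What to change.** 1. In SAP 7.9, make the Kaplan-Meier estimate at Day 365 the reported one-year all-cause mortality rate, and align 7.9 with 7.10.
2. For aneurysm-related mortality and the non-fatal events, preferably use cumulative incidence with death as a competing event, from Day 0 through 60 months, so that the 12-month and later figures lie on one curve.
3. Keep m/(m+k) as a supportive table with its denominator shown.
4. State which denominator applies to serious adverse events in 7.9 and in 7.10.

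The cost is SAP wording and minor extra programming for the cumulative incidence. Kaplan-Meier output for mortality is already planned, and the estimates use event-onset and time-in-study data that Table 5 already needs. If exit is related to risk, none of these estimators removes the bias, so the number and timing of exits should be shown beside the rates.
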